Exhibit C – SyMRI and Sickkids Project Plan

Reducing scan times and improving care through quantitative imaging:

Evaluating SyMRI in pediatric populations

[name], [name] [name]

Revision overview

New Time Frame – Until end of 2017 for additional recruitment

Expanded to include participants on Research MRI and CDIU MRI

Increase # of patients

+25 Neonatal

+75 All ages

Added [name] as co-PI

1. Lay Summary

Typical magnetic resonance imaging (MRI) involves taking many images called 'contrasts' to look at the body in different ways. Standard scan settings are usually good enough for a radiologist to review. The best settings often change with the age of the patient and their health, and are time consuming to determine. Quantified imaging is an alternative to contrast-based imaging which explicitly measures tissue properties and can be used to create almost any contrast. This method of imaging has been held back by a lack of the right software. Synthetic MR Technologies has created a quantified imaging solution - **SyMRI** - to enable radiologists to acquire quantified images and always obtain the best contrast images.

2. Objective

The objective of this study is to evaluate SyMRI in a pediatric population to determine if Sickkids would be interested in purchasing this product / support Health Canada approval. Specifically, we are interested in determining if SyMRI is clinically useful:

- Is synthetic imaging quality comparable / better than conventional imaging?
 - o Qualitative – Are radiologists more confident using synthetic MR vs conventional
 - o Quantitative – Signal-to-noise (SNR) and Contrast-to-noise (CNR)
- To what extent can total exam times be reduced?
- Is the software user friendly and would our radiologists use it?

SyMRI will be integrated in future MR systems manufactured by GE and Philips. For GE, their next MR system software releases (DB25 and Signa Pioneer) will include SyMRI as a purchasable option – FDA approval is expected in Q2 2015. Philips is targeting Q2/Q3 2015 for releasing SyMRI on its 1.5T and 3T platforms. To evaluate this product without regulatory approval (considered a Class II medical device) an Investigational Testing Authorization (ITA) must be filed with Health Canada. Local REB approval is required as part of the ITA application.

3. Background

Typical clinical MR scanning requires the imaging of multiple contrasts (T1, T2, FLAIR) to provide radiologists with sufficient data for reporting purposes. However, these contrast images typically have no quantitative value and are defined by strict acquisition parameters that are not easily adjusted. Developmental changes or pathologies which affect tissue relaxation parameters often require non-standard parameters for optimal imaging. For example, T1 relaxation times in grey matter (GM) and white matter (WM) at 1.5T will range from 2000 and 3000ms, in very preterm born neonates at birth, but will decrease to 1100 and 800ms by adulthood. The two- to three-fold decrease in relaxation times, coupled with GM-T1 becoming longer than WM-T1 with age, necessitates dramatically different imaging parameters. These changes in T1 with age, and similarly with T2, vary by subject and are very difficult to determine *a priori*. Consequently, current practise is to set general parameters by approximate age group – Neonates (<1 mth), Infants (1mth-2yr), Adolescents (2yr-12yr), and Teenagers/Adults (13+). However, as both T1, and T2 continue to change with age, and may be affected by pathology, i) **image contrast using generic parameters is often sub-optimal** and ii) **total exam times may be increased** in an attempt to improve contrast by adjusting parameters on the fly.

An alternative approach to imaging specific contrasts is to directly quantify tissue parameters – T1, T2, Proton Density (PD) – and use these quantitative parameters to generate the desired contrast images after acquisition. In doing so, i) **scan times may be reduced** as there will be no need to ‘guess’ or adjust acquisition parameters, and ii) almost **any image contrast may be generated**. Clinical adoption of quantified imaging has been hampered by the lack of an elegant pulse sequence and appropriate software that is compatible with typical clinical workflow.

Synthetic MR Technologies is attempting to address this issue by providing the **software** and the **pulse sequence** (in partnership with the major MR manufacturers) to bring MR quantification into clinical usage. The MDME sequence aims to provide whole absolute quantification of T1, T2, PD and B1 inhomogeneity in **5 minutes** at typical clinical resolution (0.8 x 0.8 x 5mm). SyMRI software then allows a user to synthesize any almost image contrast (T1, T2, PD, FLAIR, IR, DIR, etc) by adjusting imaging parameters after the fact. Conventional T1, T2, and FLAIR acquisitions would take a minimum of 12 minutes, and may need to be repeated if image contrast is poor. Not only could **total exam times be reduced**, by taking image generation offline, but **scan quality can be improved**, by enabling the examination of various contrast images that otherwise would not have been obtained.

There is great potential for this solution at the Hospital for Sick Children. A significant portion of the brain imaging performed at Sickkids involves neonates and infants, which pose a unique problem in that tissue contrast changes rapidly during this period (ideal sequence at 3 months, is less useful at 6 months). Consequently, image contrast and therefore quality is often sub-optimal. Furthermore, a combined T1, T2 and FLAIR sequence would **save at least 5 minutes** per subject. Time savings could be even greater as the need for repeat scanning due to poor contrast could be eliminated.

To explore this opportunity, Sickkids and SyMRI would like to sign an evaluation agreement in partnership with Philips and Siemens to trial the MDME sequence and SyMRI software. Philips would provide the pulse sequence. SyMRI would provide the software and technical support. Sickkids would test the sequence initially in small population of adults (6-10) and then acquire a large cohort of neonates, infants, adolescent, and teenagers.

From a regulatory perspective, SyMRI is considered a Class II medical device. To proceed with this proposal, Sickkids will be filling an application for Investigational Testing Authorization (ITA) with Health

Canada on behalf of Synthetic MR. This application requires REB approval, and as an unfunded study, the REB application requires scientific Peer Review.

Select Publications


4. Methodology

Eligible subjects (see below for criteria) will be identified by WL from patients scheduled for clinical neuro MRIs on a weekly basis. WL will approach eligible subject's parents / guardian the day of their scan to present the research study and to seek consent. Subjects who agree to participate in the study will receive an additional 5 minutes of scanning using the SyMRI pulse sequence. Their clinical scans will be review as per standard operating procedure.

Subjects enrolled in this study will have their conventional and SyMRI scans read by a radiologist/fellow trained to use SyMRI at a later date. The radiologist will alternate between viewing SyMRI or conventional MRI first for any given subject. They will be asked to rate the diagnostic utility of SyMRI as better, equal, or worse than conventional MRI. In addition they will record how long they spend review each set of images. Finally, all radiologists involved in this study will be asked to provide feedback with respect to the usability of SyMRI software.

5. Analysis

SyMRI will be primarily evaluated on its ability to generate clinically useful images, and if it can be used to reduce total scan times in all, or some, of the target age groups. A secondary output of this project will be to evaluate the usability of SyMRI software and determine if it could be reasonably integrated into a radiologist's existing workflow.

Clinical Utility – SyMRI's average rating as 'Better', 'Equal', or 'Worse' than conventional imaging will be tabulated from all reviewer responses. Assigning a value of 3, 2, and 1 respectively to these ratings – SyMRI is expected to average no lower than a 2.0 – at least equal to conventional imaging. Paired parametric (t-test) and non-parametric (wilcoxon signed-rank) statistical tests will be used to compare time spent using SyMRI vs Conventional MRI to determine if one approach is significantly faster than the other.

Quantitative Image Quality – Image SNR in WM/GM will be calculated and compared between conventional MRI and SyMRI (used to generate fixed / comparable contrasts). Paired parametric (t-test) and non-parametric (wilcoxon signed-rank) statistical tests will be used to evaluate if one approach is significantly better than the other.

Scan Time Reduction – Average scan time of SyMRI vs. Conventional MRI will be computed based on timing data stored in the MR images. A minimum of 5 minutes of scan time is expected to be saved using SyMRI.

6. Budget

No funding is required for this study. Software and installation will be provided by SyMRI and Philips at no charge. Work completed by WL will fall under his existing responsibilities.

7. Project Overview

- 1) Evaluate product performance relative to conventional T1, T2, FLAIR, qT1 and qT2
 - a) Preliminary evaluation – 6 adult volunteers (>18 years of age)
 - b) Clinical Evaluation
 - i) **25 neonates (<1 month of age)**
 - ii) **25 infants (1mth – 2 years of age)**
 - iii) **25 adolescents (2 – 12 years of age)**
 - iv) **25 teenagers (13-18 years of age)**
- 2) Evaluation
 - a) Scan Time Impact - Scan report forms, documenting time spent scanning SyMRI, vs conventional MRI.
 - b) Quantitative – Comparison of conventional and synthetic MR images using Matlab.
 - i) SNR, CNR. Repeatability of images.
 - c) Qualitative – Train radiologists / fellows to use SyMRI software. Complete questionnaire with respect to experience working with software. Diagnostic quality of SyMRI image
- 3) Data to be provided by Sickkids to SyMRI
 - a) 4 in-vivo clinical imaging datasets including conventional clinical and product protocol
 - i) De-identified DICOM images including clinical interpretation and commentary
 - ii) 2 neonatal/infant and 2 adolescent/teenager

8. Estimated Timelines / Milestones

- 1) Sequence delivery (Philips, SyMRI, Sickkids) – Q4, 2015
- 2) Software delivery / installation (SyMRI, Sickkids) – Q4, 2015
- 3) Adult acquisition and evaluation complete (Sickkids) – Q4, 2015
- 4) Clinical evaluation (Sickkids) – 5 neonates + 5 adolescents / month – Ongoing
- 5) Initial data sharing and commentary (SyMRI, Sickkids) – Q4, 2015
 - a. 1 from neonatal/infant and 1 from adolescent/teenager provided to SyMRI
- 6) Clinical acquisition complete (SyMRI, Sickkids) – Q1, 2016
 - a. 1 from neonatal/infant and 1 from adolescent/teenager provided to SyMRI
- 7) Product evaluations complete and provided to SyMRI (SyMRI, Sickkids) – Q1, 2016
- 8) Sequence delivery (Siemens, SyMRI, Sickkids) – Q1, 2017
- 9) Research Acquisition (SyMRI, Sickkids) – 2017
- 10) Clinical Acquisition (Philips, Sickkids) – 2017
- 11) Product evaluation (Sickkids, SyMRI, Siemens, Philips) – Q4 2017

9. Recruitment Considerations

Inclusion / Exclusion criteria

Any stable patient undergoing clinical MRI of the brain is eligible for this study. Only those patients where an additional 10 minutes of MR imaging would not be advisable (ie. unstable, implants) will be excluded.

Research patients undergoing research MRI of the brain for another study will be eligible. Only those subjects where an additional 10 minutes of MR imaging cannot be accommodated into their original booking will be excluded.

Risks and benefits to patients

There are no risks associated with SyMRI. The pulse sequence is a modified clinical imaging sequence and does not approach any scanner safety limits. For Philips, the sequence has been approved by the scanner manufacturers themselves and will be installed by their employees. For Siemens, the sequence will be obtained as part of a C2P agreement between Karolinska University Hospital and The Hospital for Sick Children. There is no possibility of adverse events beyond those associated with normal clinical MR imaging.

Patients involved in the validation of SyMRI may benefit from the improved diagnostic capabilities of SyMRI (custom image contrasts). This may eliminate the need for a repeat MRI session as required images may be generated through post-processing. Future patients would also benefit from reduced scan times.

Consent and data sharing

Parents / Guardians of eligible patients will be approached by WL on the day of their scan. The consent provides a lay summary of the study's rationale and objectives. SyMRI adds 5-10 minutes of scanning to the patient's MR session. There is no additional risk associated. Parents / Guardians may opt-in to share their child's data with SyMRI for evaluative purposes.

The scans for a limited number of patients (4) will be shared with SyMRI for evaluative purposes. Data will be de-identified and transferred using Sickkids' secure file transfer service according to hospital guidelines. SyMRI may not share this data with any other parties.

10. Legal

Data Transfer Agreement

SyMRI and Sickkids will sign a software evaluation agreement for this study. This agreement will cover the aforementioned objectives and timeline. Additional terms outline legal responsibilities for both parties. This document has been reviewed by legal teams for both parties.

Regulatory Approval

SyMRI has CE and ISO regulatory approval. Their product is currently undergoing regulatory approval through MR manufacturers (GE, Philips).

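### Ratings given only after both image sets are seen, and pooled over viewing order, cannot show what a reader would report from SyMRI alone

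*Protocol*

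**What the plan says.** Protocol section 4 (Methodology) sets out the reading: "Subjects enrolled in this study will have their conventional and SyMRI scans read by a radiologist/fellow trained to use SyMRI at a later date". On order: "The radiologist will alternate between viewing SyMRI or conventional MRI first for any given subject". On the outcome: "They will be asked to rate the diagnostic utility of SyMRI as better, equal, or worse than conventional MRI". On time: "In addition they will record how long they spend review each set of images".

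Protocol section 5 and the Analysis part of the SAP code the ratings 3, 2 and 1. The ratings "will be tabulated from all reviewer responses", and "SyMRI is expected to average no lower than a 2.0". Neither document gives a test, interval or margin for this mean, or a split by which set was opened first. For time, "Paired parametric (t-test) and non-parametric (wilcoxon signed-rank) statistical tests will be used to compare time spent using SyMRI vs Conventional MRI", again without a term for order.

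Protocol section 7 and the SAP's evaluation list also name the diagnostic quality of the SyMRI images as a qualitative item, but do not say when or how it is collected. Neither document asks for findings per image set, an entry closed before the second set is opened, an interval between the two sets, or a reference standard.

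The purpose is in Protocol section 3: "Conventional T1, T2, and FLAIR acquisitions would take a minimum of 12 minutes", against 5 minutes for the SyMRI sequence, with a claimed saving of at least 5 minutes per subject.

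**The concern.** During the study SyMRI is an extra scan, so it saves time in later practice only if the conventional T1, T2 and FLAIR scans are then left out. The evidence needed for that step is what a reader would report with SyMRI and nothing else.

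A comparative rating can be given only after both sets have been seen. When the conventional set comes first, the reader opens SyMRI knowing what is there and where. When SyMRI comes first, an unaided SyMRI view does take place, but only its duration is recorded. Averaging the two orders mixes aided and unaided views. If SyMRI is somewhat poorer on its own, which is the case the 2.0 threshold should expose, carry-over can bring the mean closer to the threshold. The study also could not say how often SyMRI alone would have led to a different report.

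**Working it through.** The documents state no power, alpha or margin for the rating, so there is no planned figure to reproduce. The check asks how far carry-over could move the pooled mean.

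**Inputs from the documents.** Four age groups of 25 give 4 × 25 = 100 children (Protocol section 7, SAP). Even alternation puts about 50 in each order, or 12 to 13 per age group. Ratings are 3, 2 or 1 and the threshold is 2.0 (section 5, SAP).

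**Assumed inputs (in neither document).**
- mS: share of children in whom SyMRI alone would miss a finding that conventional shows.
- mC: the reverse.
- h: share of such misses masked when that set is viewed second. h = 0 is no carry-over and h = 1 is full masking.
- An unmasked miss moves the rating by one step. All other children are rated Equal.

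**Expected mean rating.**
- SyMRI first: 2 − mS + mC(1 − h)
- Conventional first: 2 − mS(1 − h) + mC
- Equal halves pooled: 2 − (mS − mC)(1 − h/2)

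The deficit is therefore multiplied by 1 − h/2: unchanged at h = 0 and halved at h = 1. If mS = mC the pooled mean stays at 2.0 whatever h is.

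**Results.** P is the chance that the observed mean reaches 2.0, by exact convolution of the three-point ratings (50/50 split for N = 100, 13/12 for N = 25). Means are for equal halves.

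| mS | mC | h | SyMRI first | Conv. first | Pooled | P, N = 100 | P, N = 25 |
|---|---|---|---|---|---|---|---|
| 5% | 0 | 0 | 1.95 | 1.95 | 1.95 | 0.006 | 0.277 |
| 5% | 0 | 0.5 | 1.95 | 1.975 | 1.9625 | 0.022 | 0.379 |
| 5% | 0 | 1 | 1.95 | 2.00 | 1.975 | 0.077 | 0.513 |
| 10% | 0 | 0 | 1.90 | 1.90 | 1.90 | 0.000 | 0.072 |
| 10% | 0 | 1 | 1.90 | 2.00 | 1.95 | 0.005 | 0.254 |
| 10% | 5% | 0 | 1.95 | 1.95 | 1.95 | 0.119 | 0.350 |
| 10% | 5% | 1 | 1.90 | 2.05 | 1.975 | 0.221 | 0.454 |
| 5% | 5% | 1 | 1.95 | 2.05 | 2.00 | 0.594 | 0.688 |

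The third row can be checked by hand. With mC = 0 and h = 1, the mean reaches 2.0 only if no SyMRI-first child is rated Worse: 0.95^50 = 0.077 and 0.95^13 = 0.513.

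**A larger deficit.** With mS = 15%, mC = 0 and h = 1, the pooled mean is 2 − 0.15 × 0.5 = 1.925 instead of 1.85. Both lie below 2.0, and the chance of reaching 2.0 with 100 children is 0.85^50 ≈ 0.0003.

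**Reading time.** The second set is read with knowledge of the first. A constant gain from coming second cancels in the mean paired difference when the orders are equal in number. It does not cancel if the gain differs between the two sets, and the planned paired tests would not show it.

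**The case against.** The best defence is that the plan asks a comparative question. Protocol section 2 asks whether synthetic image quality is comparable or better and whether radiologists are more confident with it. A comparative rating needs both sets in view, and alternation is a recognised counterbalance. This stands for the rating itself, which should stay. It does not cover the step from the rating to replacement, on which the time saving depends.

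Several further points stand and limit the concern:

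- Carry-over is a plausible mechanism, not a documented fact. The documents set no interval between the sets, but they also do not say that both are read in one sitting.
- A lesion that is fainter on SyMRI can still be rated Worse by a reader who knows it is there, and one that is invisible stays invisible. Full masking is the extreme case.
- The effect works both ways: conventional misses can be masked in the SyMRI-first half.
- Protocol section 9 admits any stable patient having a clinical brain MRI, and research subjects. Children without abnormalities cannot contribute missed findings, and no prevalence is given.

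A reader might infer that SyMRI's misses are in fact concealed in half of the children, or that the design would pass an inferior SyMRI. The documents support neither. They give no miss rates, and in the 15-point illustration the pooled mean stays below 2.0 even under full masking.

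**Conclusion.** The point holds as a cheap improvement, in two parts.

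The first rests on the documents alone. No findings are recorded from either set before the other is opened, so the study cannot report what a reader concludes from SyMRI by itself. Ratings and times are also analysed without regard to order.

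The second is conditional. If SyMRI is weaker and knowledge carries over, the pooled deficit shrinks by the factor 1 − h/2, so by half at most. For an assumed 5-point deficit with mC = 0, full masking raises the chance of reaching 2.0 from 0.006 to 0.077 with 100 children, and from 0.277 to 0.513 in one age group of 25. The age-group figure matters because section 5 asks about all or some of the groups. All of these values rest on assumed rates. The attenuation when SyMRI is weaker follows from carry-over; its size is unknown. It would be wrong to conclude that the bias always favours SyMRI or that the pooled result is invalid.

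**What to change.** **Protocol section 4.** After the first-opened set, the reader records which set it was, the main findings, and whether that set alone is sufficient for a report. The entry is locked before the second set is opened, and is made without the clinical report in view. The reading-time clock stops before the entry, so that it does not lengthen the first set's recorded time. The comparative rating stays at the end.

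**SAP.**
- Report the 3/2/1 rating and the reading times by which set was opened first, beside the pooled results.
- Where a routine clinical report exists, give with 95% intervals the proportion of SyMRI-first reads whose main findings agree with it.
- Give the same proportion for conventional-first reads as a between-reader benchmark. Both proportions then use one reference. Checking a conventional-first read against the study's own conventional read would be circular.
- State that the clinical report comes from the conventional images, so the benchmark favours conventional.

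**Cost.** No extra scan, reader or reading session is needed. The work is a short form entry per child, a definition of main findings, and a rule for judging agreement. Precision is limited. At assumed agreement of 95% and 80% with 50 children per order, the half-width on the difference is 1.96 × √(0.95 × 0.05/50 + 0.80 × 0.20/50) = 0.126, roughly ±13 points. It is wider within age groups, and fewer children will have abnormalities. The comparison should be labelled descriptive, and any claim about replacement limited accordingly.

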SyMRI Statistical Analysis Plan

Reducing scan times and improving care through quantitative imaging:

Evaluating SyMRI in pediatric populations

[name], [name], [name]

Analysis

SyMRI will be primarily evaluated on its ability to generate clinically useful images, and if it can be used to reduce total scan times in all, or some, of the target age groups. A secondary output of this project will be to evaluate the usability of SyMRI software and determine if it could be reasonably integrated into a radiologist's existing workflow.

Clinical Utility – SyMRI's average rating as 'Better', 'Equal', or 'Worse' than conventional imaging will be tabulated from all reviewer responses. Assigning a value of 3, 2, and 1 respectively to these ratings – SyMRI is expected to average no lower than a 2.0 – at least equal to conventional imaging. Paired parametric (t-test) and non-parametric (wilcoxon signed-rank) statistical tests will be used to compare time spent using SyMRI vs Conventional MRI to determine if one approach is significantly faster than the other.

Quantitative Image Quality – Image SNR in WM/GM will be calculated and compared between conventional MRI and SyMRI (used to generate fixed / comparable contrasts). Paired parametric (t-test) and non-parametric (wilcoxon signed-rank) statistical tests will be used to evaluate if one approach is significantly better than the other.

Scan Time Reduction – Average scan time of SyMRI vs. Conventional MRI will be computed based on timing data stored in the MR images. A minimum of 5 minutes of scan time is expected be saved using SyMRI.

Evaluation:

- 1) Evaluate product performance relative to conventional T1, T2, FLAIR, qT1 and qT2
 - a) Preliminary evaluation – 6 adult volunteers (>18 years of age)
 - b) Clinical Evaluation
 - i) **25 neonates (<1 month of age)**
 - ii) **25 infants (1mth – 2 years of age)**
 - iii) **25 adolescents (2 – 12 years of age)**
 - iv) **25 teenagers (13-18 years of age)**
- 2) Evaluation
 - a) Scan Time Impact - Scan report forms, documenting time spent scanning SyMRI, vs conventional MRI.
 - b) Quantitative – Comparison of conventional and synthetic MR images using Matlab.
 - i) SNR, CNR. Repeatability of images.

- c) Qualitative – Train radiologists / fellows to use SyMRI software. Complete questionnaire with respect to experience working with software. Diagnostic quality of SyMRI image
- 3) Data to be provided by Sickkids to SyMRI
- a) 4 in-vivo clinical imaging datasets including conventional clinical and product protocol
 - i) De-identified DICOM images including clinical interpretation and commentary
 - ii) 2 neonatal/infant and 2 adolescent/teenager

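### The primary clinical-utility ratings have no interval or test, so an average of 2.0 does not by itself show that SyMRI is at least equal to conventional MRI

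*SAP*

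**What the plan says.** The SAP's Analysis section opens by stating that "SyMRI will be primarily evaluated on its ability to generate clinically useful images", alongside scan-time reduction. Under Protocol section 4 (Methodology), each enrolled subject has both sets of "scans read by a radiologist/fellow trained to use SyMRI". The reader is asked to "rate the diagnostic utility of SyMRI as better, equal, or worse than conventional MRI", which gives one direct comparative rating.

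The SAP's Clinical Utility paragraph, repeated in Protocol section 5, says the average rating "will be tabulated from all reviewer responses". The scoring is given as "Assigning a value of 3, 2, and 1 respectively to these ratings", and the benchmark is "SyMRI is expected to average no lower than a 2.0", which the same sentence equates with equality or better against conventional MRI.

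The same paragraph names a paired t-test and a Wilcoxon signed-rank test, but for the time spent reading each image set. The next paragraph names the same two tests for SNR. Neither document gives a confidence interval, hypothesis test, margin, alpha level or sample-size basis for the ratings.

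**The concern.** The plan tests reading time and SNR but attaches no uncertainty to the ratings, which belong to the primary evaluation. It also equates a point average of 2.0 with being at least as good as conventional imaging. Two things are lost:

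- **Sampling error.** A sample average of 2.0 is compatible with a true mean below 2.0.
- **The make-up of the average.** All ratings Equal, and half Better with half Worse, both give 2.0. For diagnostic utility these are very different findings.

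Protocol section 2 says the results will show whether the hospital would be "interested in purchasing this product / support Health Canada approval". What is at stake is therefore an unsupported product conclusion. No enrolled child's care depends on the rating, because clinical scans are reviewed in the usual way (Protocol section 4).

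**Working it through.** **Inputs from the documents.** Scores 3/2/1; benchmark 2.0; four age groups of 25, so 4 × 25 = 100. The Protocol's revision overview adds 25 neonates and 75 subjects of all ages without saying whether the listed 100 already includes them, so n = 200 is shown as well.

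**Assumptions.** One independent rating per subject. The documents give no expected rating frequencies, so every Worse/Equal/Better split below is assumed. There is no power or sample-size figure in the plan to reproduce.

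**Step 1: what 2.0 means.** Mean = 3·P(B) + 2·P(E) + 1·P(W). Since P(E) = 1 − P(B) − P(W), this reduces to 2 + P(B) − P(W). The benchmark is met exactly whenever P(B) = P(W), so P(Worse) can be anything from 0% to 50%. At n = 100, a mean of exactly 2.0 can go with any of these (Clopper-Pearson 95% limits):

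| Worse | 95% limits |
|---|---|
| 0% | 0% to 3.6% |
| 10% | 4.9% to 17.6% |
| 25% | 16.9% to 34.7% |
| 50% | 39.8% to 60.2% |

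**Step 2: precision at an observed mean of 2.0.** The variance of one rating is P(B) + P(W) − (P(B) − P(W))². At mean 2.0 this is d, the share of ratings that are not Equal. Using the sample SD, the 95% half-width is t × √(d/(n − 1)). For n = 100 and d = 0.5: 1.984 × √(0.5/99) = 0.141, so the lower limit is 2.0 − 0.141 = 1.86.

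| d | Lower limit, n = 100 | Lower limit, n = 200 | Half-width, n = 25 |
|---|---|---|---|
| 0.2 | 1.91 | 1.94 | 0.19 |
| 0.5 | 1.86 | 1.90 | 0.30 |
| 1.0 | 1.80 | 1.86 | 0.42 |

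**Step 3: chance of averaging 2.0 or more when the true mean is lower.** This is the exact probability that Better ratings at least equal Worse ratings in number, from the n-fold convolution of the three-category distribution.

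| True mean | Split W/E/B (%) | n = 100 | n = 200 |
|---|---|---|---|
| 1.95 | 15/75/10 | 18.2% | 8.8% |
| 1.95 | 20/65/15 | 22.2% | 12.7% |
| 1.95 | 30/45/25 | 27.1% | 18.2% |
| 1.90 | 15/80/5 | 1.3% | 0.07% |
| 1.90 | 20/70/10 | 3.8% | 0.5% |
| 1.90 | 30/50/20 | 8.8% | 2.5% |
| 1.90 | 40/30/30 | 12.7% | 4.9% |
| 1.80 | 30/60/10 | 0.06% | <0.01% |
| 1.80 | 60/0/40 | 2.7% | 0.26% |

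More extreme splits widen these ranges. For a true mean of 1.95 at n = 100, 5/95/0 gives 0.6% and 52.5/0/47.5 gives 34%. For 1.90, 55/0/45 gives 18%.

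**Step 4: single age groups.** At n = 25 a true mean of 1.80 still averages 2.0 or more with probability 7% (30/60/10) to 15% (60/0/40).

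**The case against.** The strongest reply is that no decision rule is being misused. The text says "SyMRI is expected to average no lower than a 2.0" as an expectation, in the same form as the expected scan-time saving, and the plan claims no hypothesis, alpha or margin anywhere. That is fair. But 2.0 is the only benchmark the ratings have, and the SAP itself supplies the reading that it means at least equal.

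Second, tabulating a three-category response most naturally yields counts. If counts are published, the hidden-Worse problem largely goes away and a reader could compute an interval. This part stands as a possibility. However, the grammatical subject of the sentence is the average rating, so the intention is unclear, and published counts alone would not remove the equality reading.

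Third, this is an unfunded product evaluation at one hospital in which the rating is one input among several, and a large overall deficit would show. That stands too: at n = 100 a true mean of 1.80 slips through at most 2.7% of the time. Only deficits of about 0.05 to 0.10 points are likely to be missed, and the documents do not say whether a deficit of that size matters.

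Finally, the probabilities in Step 3 hold only for the named splits, and n = 200 is uncertain. Neither changes the conclusion.

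**Conclusion.** The concern holds. As written, the plan would let a bare average of 2.0 be reported as at least equal to conventional imaging. At n = 100 the 95% lower limit in that case is about 1.80 to 1.91, and the proportion rated Worse could be anything up to half. The exposure is to slight inferiority, or to a substantial Worse share offset by Better ratings; a large overall deficit is unlikely to be hidden. The sizes rest on one independent rating per subject and on assumed splits. That the plan attaches no measure of uncertainty to the ratings does not depend on those assumptions. It should be corrected before analysis. It is not a threat to participants.

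**What to change.** 1. Report Better, Equal and Worse as counts and percentages with exact 95% intervals. Report the mean, or equivalently P(Better) − P(Worse), with a 95% interval, overall and descriptively by age group. If every rating were Equal, the t interval would have zero width; the exact interval for Worse would still be informative.
2. Remove the reading of a point average of 2.0 as equality. Base the statement on the 95% interval and the proportion Worse, and call it descriptive.
3. Optional: if the sponsor sets and justifies a margin before analysis, compare the lower confidence limit with it.
4. Conditional: the Methodology wording suggests one reader per subject. If any subject is read by more than one, average to one score per subject first, because ratings of the same subject are correlated.

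Items 1 and 2 are the core of the fix. The cost is a change of SAP wording and a few lines of analysis, with no new data.

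The downside is that a claim of equality becomes harder to reach. With half the ratings not Equal, the whole 95% interval lies at or above 2.0 only from a net Better minus Worse of +14 in 100 (mean 2.14) or +20 in 200 (mean 2.10). With 25 per group the half-widths are 0.19 to 0.42, so age-group results should stay descriptive.
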